# 14. DIRECT ACCESS TO SOURCE DATA/DOCUMENTS

# 14.1. Study Monitoring

Unless otherwise waived or addressed in another forum (eg, investigator meeting), before an investigational site can enter a participant into the study, a representative of Sage will visit the investigational study site to:

- Confirm the adequacy of the facilities
- Discuss with the investigator(s) and other personnel their responsibilities with regard to protocol adherence, IP management, GCP/ICH GCP compliance, and the responsibilities of Sage or its representatives. Agreed upon site responsibilities will be documented in a Clinical Trial Agreement between Sage and the investigator.

During the study, a monitor from Sage or representative will have regular contacts with the investigational site, for the following:

- Provide information and support to the investigator(s)
- Confirm that facilities remain acceptable
- Confirm that the investigational team is adhering to the protocol, that data are being accurately recorded in the eCRF, and that IP accountability checks are being performed
- Perform source data verification. This includes a comparison of the data in the eCRF with the participant's medical records at the hospital or practice, and other records relevant to the study. This will require direct access to all original records for each participant (eg, medical records, source documents, clinic charts).
- Record and report any protocol deviations not previously sent to Sage Therapeutics.
- Confirm AEs and SAEs have been properly documented on eCRFs and confirm any SAEs have been forwarded to Sage Therapeutics and those SAEs that met criteria for reporting have been forwarded to the IRB or IEC.

The monitor will be available between visits if the investigator(s) or other staff needs information or advice.

# 14.2. Audits and Inspections

Sage Therapeutics or authorized representatives of Sage Therapeutics, a regulatory authority, or an IEC/IRB may visit the site to perform an audit(s) or inspection(s), including source data verification. The purpose of a Sage Therapeutics audit or a regulatory authority inspection is to systematically and independently examine all study-related activities and documents to determine whether these activities were conducted, and data were recorded, analyzed, and accurately reported according to the protocol, GCP/ICH GCP guidelines, and any applicable regulatory requirements. The investigator should contact Sage Therapeutics immediately at [contact] if contacted by a regulatory agency or IRB/IEC about an inspection.

# 14.3. Institutional Review Board or Independent Ethics Committee

The principal investigator must obtain IRB (or IEC) approval for the clinical study prior to enrolling a participant. Initial IRB (or IEC) approval, and all materials approved by the IRB (or IEC) for this study including the participant consent form and recruitment materials must be maintained by the investigator and made available for inspection.

# **15. QUALITY CONTROL AND QUALITY ASSURANCE**

To ensure compliance with GCP and all applicable regulatory requirements, Sage Therapeutics may conduct a quality assurance audit(s) at the clinical site. Please see Section 14.2 for more details regarding the audit process.

The investigator must have adequate quality control practices to ensure that the study is performed in a manner consistent with the protocol, GCP/ICH GCP guidelines, and applicable regulatory requirements. The investigator is responsible for reviewing all identified protocol deviations. Protocol deviations that harm or increase the possibility of harm to the rights and welfare of a participant, or a deviation made without prior IRB/IEC approval to eliminate an immediate hazard to the participant should be reported to the IRB/IEC per the IRB/IEC's written procedures.

The investigator is responsible for supervising any individual or party to whom the investigator delegates study-related duties and functions conducted at the study site. When the investigator retains the services of any individual or party to perform study-related duties and functions, the investigator must ensure the individual or party is qualified to perform study-related duties and functions and should implement procedures to ensure the integrity of the study-related duties and functions performed, and any data generated.

The investigator must maintain adequate and accurate source documents and study records that include all pertinent observations on each of the site's study participants. Source data must be attributable, legible, contemporaneous, original, accurate, and complete. Changes to source data should be traceable, should not obscure the original entry, and should be explained, if necessary to provide clarification.

# 16. ETHICS

# 16.1. Ethics Review

The final study protocol, including the final version of the ICF, must be given a written and dated approval or favorable opinion by an IRB or IEC as appropriate. The investigator must obtain and document approval before he or she can enroll any participant into the study. The IRB or IEC must supply to the sponsor a list of the IRB/IEC membership and a statement to confirm that the IRB/IEC is organized and operates according to GCP and applicable laws and regulations.

The principal investigator is responsible for informing the IRB or IEC of any amendment to the protocol in accordance with local requirements. In addition, the IRB or IEC must approve all advertising used to recruit participants for the study. The protocol must be re-approved by the IRB or IEC upon receipt of amendments and annually, as local regulations require.

The principal investigator is also responsible for providing the IRB or IEC with reports of any reportable serious adverse drug reactions from any other study conducted with the IP. Sage Therapeutics will provide this information to the principal investigator.

Progress reports and notifications of serious adverse drug reactions will be provided to the IRB or IEC according to local regulations and guidelines. In addition, the principal investigator must inform the IRB/IEC and sponsor of any changes significantly affecting the conduct of the study and/or increasing the risk to participants (eg, violations to the protocol or urgent safety measures taken for participant safety).

# 16.2. Ethical Conduct of the Study

The study will be performed in accordance with ethical principles that have their origin in the Declaration of Helsinki and are consistent with ICH and GCP guidelines, as well as all applicable regional or national regulatory requirements.

# 16.3. Written Informed Consent

Prior to enrolling a study participant, the investigator(s) will ensure that the participant is given full and adequate oral and written information about the nature, purpose, possible risk and benefit of the study. Participants must also be notified that they are free to discontinue from the study at any time. The participant should be given the opportunity to ask questions and allowed time to consider the information provided.

When the participant decides to participate in the study, the participant (or the participant's, parent or legally authorized representative) must provide signed and dated informed consent that is approved by the IRB/IEC for this protocol. The written consent must be obtained before conducting any study procedures. The investigator must document the consent process in the participant's source records. The investigator must maintain the original, signed ICF. A copy of the signed ICF must be given to the participant or to the participant's parent or legally authorized representative.

Throughout the study participants should be informed of any changes made to the study and as new safety and or risk information becomes known. The provision of this information will be

documented in the participant's source records, and when applicable, an updated ICF will be provided.

# 17. DATA HANDLING AND RECORDKEEPING

# 17.1. Inspection of Records

Sage Therapeutics or its representative(s) will be allowed to conduct site visits at the investigation facilities for the purpose of monitoring any aspect of the study. The investigator agrees to allow the monitor to inspect the facility, drug storage area, drug accountability records, participant charts and study source documents, and other records relative to study conduct.

Inspection of the study by a Regulatory Authority may occur at any time. The investigator must agree to the inspection of study-related records and source documents by the Regulatory Authority representative(s).

# 17.2. Retention of Records

The principal investigator must maintain all documentation relating to the study for the period outlined in the site contract, or for a period of 2 years after the last marketing application approval, and until there are no pending or contemplated marketing applications in an ICH region or at least 2 years have elapsed since the formal discontinuation of clinical development of the IP. Sage is responsible to inform the investigator/institution as to when study documents no longer need to be retained.

# **18. PUBLICATION POLICY**

All information concerning SAGE-718 is considered confidential and shall remain the sole property of Sage Therapeutics. The investigator agrees to use this information only in conducting the study and shall not use it for any other purposes without written approval from Sage Therapeutics. No publication or disclosure of study results will be permitted except as specified in a separate, written, agreement between Sage Therapeutics and the investigator.

#### Date of Amendment: 22 December 2023

#### A Randomized, Double-blind, Placebo-controlled Study to Evaluate the Effects of SAGE-718 in Participants with Mild Cognitive Impairment or Mild Dementia Due to Alzheimer's Disease

#### **Rationale for Protocol Amendment**

The primary purpose for this protocol amendment is to address the following recommendations, queries, emerging study results or correction of inadvertent errors, including:

- Increased the duration of the Screening Period to up to 4 weeks (Days -35 to Day -8) to increase flexibility for participants to complete the screening assessments within the time frame (Synopsis, Schedule of Assessments [Table 2]).
- Revised the duration of the Baseline Period to be "up to 1 week" to allow flexibility (Synopsis, Figure 1).
- The study schematic was updated to reflect changes in Screening Period and Baseline Period durations (Synopsis, Figure 1).
- •
- Increased the window for the Day 84 Visit and the Day 112 Follow-up Visit to ±7 days to increase flexibility and removed language that no dosing is permitted beyond Day 84 (Synopsis, Schedule of Assessments [Table 2],

, Section 5.2, Section 7.1, Section

7.1.3, Section 7.3).

- Throughout the protocol, text referring to study days was updated to reflect the corresponding study visit and window for clarity.
- The optional, **Sector 11.3.4** was removed throughout the protocol (Synopsis, Schedule of Assessments [Table 2], previous Section 11.3.4). Based on resourcing and time considerations, the team is considering alternate options to collect participant experience data outside study protocol.
- Corrected the randomization text to state that approximately 150 participants will be randomized, instead of dosed, to obtain up to 60 evaluable participants per treatment arm (Synopis, Section 7.2).
- The following changes were made to the Inclusion and Exclusion Criteria (Synopsis, Section 8.1, Section 8.2):
  - Inclusion criterion #6 was revised to add years of education adjustment for Montreal Cognitive Assessment (MoCA).

- Exclusion criterion #5 was revised to remove "clinically significant" from intracranial abnormality.
- Exclusion criterion #9 was revised to ensure participants at risk are identified and to provide clarity to investigators on suicidal behavior and ideation that leads to exclusion.
- Exclusion criterion #10b was revised to remove specific ranges for vital signs to ensure the vital signs are reviewed for clinical significance based on the population being studied by the investigator.
- Exclusion criterion #15 was added to exclude participants to plan to undergo surgery during study participation.
- Exclusion criterion #16 was added to excluded participants with a history of gastric bypass.
- Sample size text was revised to describe that an interim analysis may be performed, as one is not currently planned to perform due to fast participant enrollment (Synopsis, Section 13.8). The original protocol planned to perform one interim analysis and one final analysis using the group sequential method, and the significance level was based on the type I error spending function of Lan and DeMets to maintain the overall 0.05 significance level. Therefore, the interim analysis portion will remain in the sample size section of the protocol and will be addressed in the SAP. The original sample size was estimated based on two-sided test using an overall significance level of 0.05 and sample size will not be impacted by removing the interim analysis. The final analysis will be performed at the 2-sided significant level of 0.05.
- The description of the planned interim analysis was removed (Section 13.8.1).
- The data analysis set descriptions were updated to provide more detail (Synopsis, Section 13.1).
- An updated description of the results from Study 718-CNA-201 was added to the Introduction (Section 5).
- The description of adverse events was updated in the Benefit Risk section (Section 5.1).
- The description of the Follow-up Period was revised to include some cognition , which were inadvertently omitted (Section 7.1.4).
- Acceptable forms of contraception were updated to align with the SAGE-718 program (Section 9.2.4).

- The statement that body mass index "will be calculated" was changed to "will be derived" to indicate it will be done as part of the analyses (Section 12.1.4).
- The Overdose section was replaced with the Special Considerations section, which was implemented via Administrative Letter #1, and it is being formally added to the protocol with this amendment (Section 12.4).
- The Efficacy Analysis section was revised to simplify the list of endpoints and add a description of the covariance matrix (Section 13.5).
- Sunwoo et al, included in error, was removed from the list of references (Section 19).
- Minor textual changes have been made throughout the protocol to increase clarity on the procedures of the study.
- Study personnel and related administrative changes have been made based on changes to the study team.

Corrections to typographical errors, punctuation, grammar, abbreviations, and formatting have been made.

# 1. LIST OF ABBREVIATIONS

The following abbreviations and specialist terms are used in this Statistical Analysis Plan.

Table 1:Abbreviations and Specialist Terms

Abbreviation	Definition
AD	Alzheimer's Disease
AE	adverse event
ANCOVA	Analysis of Covariance
ATC	Anatomical Therapeutic Chemical code
BMI	Body Mass Index
BLQ	Below Limit of Quantification
CDR	Clinical Dementia Rating
CI	Confidence Intervals
COVID-19	Coronavirus Disease 2019
CS	Clinically Significant
ET	Early Termination
eCRF	electronic Case Report Form
FAS	Full Analysis Set
IA	Interim Analysis
IP	Investigational Product
IRT	Interactive Response Technology
LSM	Least Squares Means
MAR	Missing At Random
MCI	Mild Cognitive Impairment
MedDRA	Medical Dictionary for Regulatory Activities
MI	Multiple Imputation
MMRM	Mixed-effects Model for Repeated Measures

Abbreviation	Definition
MNAR	Missing Not At Random
NMDA	N-methyl-D-aspartate
PCS	Potentially Clinically Significant
PMM	Pattern Mixture Model
РТ	Preferred Term
Q1	25th percentile
Q2	75th percentile
SAE	Serious Adverse Events
SAP	Statistical Analysis Plan
SD	Standard Deviation
SE	Standard Error
SOC	System Organ Class
TEAE	Treatment-Emergent Adverse Events
WAIS-IV	Wechsler Adult Intelligence Scale Fourth Edition-IV

# 2. INTRODUCTION

This statistical analysis plan (SAP) is for the final analysis, and is based on the following approved study documents:

- Study Protocol, Version 2.0 (22 December 2023)
- electronic Case Report Form (eCRF), Version 7.0 on 29 April 2024

This SAP addresses the objectives of the study and describes the planned statistical analyses and data presentations. All analyses and data presentations will be generated using the SAS Software Version 9.4 or higher (SAS Institute, Cary, North Carolina, USA). This SAP will be finalized and approved before the clinical database lock. Any changes made to the SAP after the clinical database lock will be documented and discussed in the clinical study report for this study.

# **3. STUDY OBJECTIVES**

### **3.1. Primary Objective**

• To evaluate the effect of SAGE-718 on cognitive performance in participants with Alzheimer's Disease (AD)

# **3.2.** Secondary Objectives

• To evaluate the safety and tolerability of SAGE-718 softgel lipid capsule in participants with AD

# 3.3.

• To evaluate the safety and tolerability of SAGE-718 softgel lipid capsule on other safety parameters

# 4. STUDY ENDPOINTS

# 4.1. Efficacy Endpoint

### 4.1.1. Primary Efficacy Endpoint

The primary endpoint is the change from baseline to Day 84 in the Wechsler Adult Intelligence Scale Fourth Edition-IV (WAIS-IV) Coding Test, total correct score.

### 4.2. Safety Endpoints

- To evaluate the safety and tolerability of SAGE-718 softgel lipid capsule in participants with AD
  - Proportion of participants experiencing treatment-emergent adverse events (TEAEs) and severity of TEAEs
  - Number of participants who withdraw due to adverse events (AEs)
- To evaluate the safety and tolerability of SAGE-718 softgel lipid capsule on other safety parameters
  - Change from baseline in vital signs, clinical laboratory parameters, electrocardiograms (ECGs),

# 5. STUDY DESIGN

# 5.1. Overall Design

This is a randomized, double-blind, placebo-controlled study to evaluate the effects of SAGE-718 in participants with MCI or mild dementia due to AD. Eligible participants with a confirmed diagnosis and who meet the criteria for MCI or Mild Dementia due to AD at Screening will be randomized to receive either SAGE-718 or matching placebo. Within the SAGE-718 treatment arm, participants will receive 1.2 mg of SAGE-718 as a softgel lipid capsule orally once daily for the first 6 weeks (Days 1 Visit to 42 Visit [±2 days]), followed by 0.9 mg of SAGE-718 for the remainder of the Treatment Period (i.e., beginning the first day after the Day 42 Visit). Dosing ends at the Day 84 Visit (±7 days). The placebo arm will receive placebo throughout the Treatment Period (12 weeks).

### 5.1.1. Screening Period

The Screening Period will begin with the informed consent process for prospective participants and their study partners. Subsequent screening assessments will be performed between Day -35 and Day -8 to determine eligibility, including assessments of cognitive function. An adult study partner is required to support completion of study activities and to answer questions about the participant's condition.

### 5.1.2. Baseline Period

The Baseline Period will occur from Day -7 through Day -1. During the Baseline Period, participants will visit the clinic for collection of baseline cognitive,

data. Participants and their study partners will receive training on the study procedures and devices.

### 5.1.3. Treatment Period

The blinded Treatment Period will occur from the Day 1 Visit through the Day 84 Visit ( $\pm 7$  days). Eligible participants will be randomized 1:1 to receive either SAGE-718 or matching placebo. Participants who are randomized to SAGE-718 will receive 1.2 mg of SAGE-718 for the first 6 weeks (Days 1 Visit to 42 Visit [ $\pm 2$  days]) followed by 0.9 mg of SAGE-718 for the remainder of the Treatment Period (i.e., beginning the first day after the Day 42 Visit). Dosing ends at the Day 84 Visit ( $\pm 7$  days). All participants will self-administer blinded IP once per day in the morning, orally.

At scheduled clinic visits during the Treatment Period, safety, efficacy,

will be performed. Participants will self-administer IP in the clinic under the supervision of study staff. Participants will receive a sufficient amount of IP for daily administration until the next scheduled clinic visit, at which time study staff will assess participant adherence by examining used packaging and counting returned capsules.

During the Treatment Period, participants will be able to receive IP if there are no doselimiting safety/tolerability concerns. Participants who discontinue IP should complete the

remaining study visits as scheduled unless the participant chooses to withdraw their consent or loses the capacity to grant consent. If a participant withdraws from the study/stops study participation early, an Early Termination Visit will be conducted. Treatment with SAGE-718 can be ended without down titration.

### 5.1.4. Follow-up Period

After completing the Treatment Period, participants will return to the clinic for a Follow-up Visit on Day 112 ( $\pm$ 7 days) to collect safety, some cognition,

### Figure 1: Study Schematic

Coding Test = Wechsler Adult Intelligence Scale-IV Coding Test. See Appendix A for specific schedule of each test.

# 5.2. Sample Size and Power

The sample size calculation is based on change from baseline in WAIS-IV Coding Test total correct score. Based on data from a previous study (718-CNA-201), the assumed difference between placebo and the SAGE-718 group at the end of treatment (at Day 84) for the primary endpoint of WAIS-IV Coding test total correct score is 2.5, and the standard deviation is 4.2.

The total sample size of 120 evaluable participants will provide 90% power to detect the treatment difference of 2.5 in change from baseline in WAIS-IV Coding Test total correct score while allowing for 1 interim analysis (IA) and 1 final analysis. This sample size and power are based on a 2-sided t-test using an overall significance level of 0.05. One formal IA

may be conducted after approximately 60 participants as total have completed Day 84 (Week 12). The group sequential method by O'Brien and Fleming for the two-sided test will be used. The significance level will be based on the type I error spending function of Lan and DefsMets such that the overall significance level will be maintained at 0.05. Assuming a 20% dropout and a 1:1 randomization ratio, approximately 150 randomized participants (75 per treatment group) will be required to obtain 60 evaluable participants per treatment group. Evaluable participants are defined as those randomized participants who receive IP and have a valid baseline and at least 1 postbaseline WAIS-IV Coding test assessment. Additional participants may be randomized if the dropout rate is higher than 20%. Table 2 summarizes operating characteristics of this design based on 120 evaluable participants.

Repeated Analyses	Information Time	Number of Participants	Boundaries for Efficacy (Z-score)	Boundary for Futility (Z-score)
Interim	0.5	60	2.796	0.4229
Final	1	120	1.977	

Table 2:Group Sequential Design

\* Using the SAS Software Version 9.4

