# 13.8. Sample Size and Power

The sample size calculation is based on change from baseline in WAIS-IV Coding Test total correct score. Based on data in a previous study, we assume difference between placebo and the SAGE-718 group at the end of treatment (at Day 84) for primary endpoints of WAIS-IV Coding test total correct score is 2.5, the standard deviation is 4.2.

The total sample size of 120 evaluable participants will provide 90% power to detect the treatment difference of 2.5 in change from baseline in WAIS-IV Coding Test total correct score while allowing for one interim analysis and one final analysis. This sample size and power are based on a two-sided test using an overall significance level of 0.05. One formal interim analysis may be conducted after approximately 60 participants have completed Week 12. The group sequential method by O'Brien and Fleming for the two-sided test will be used. The significance level will be based on the type I error spending function of Lan and DeMets such that the overall significance level will be maintained at 0.05. Assuming a 20% dropout and a 1:1 randomization ratio, approximately 150 randomized participants (75 per treatment group) will be required to obtain 60 evaluable participants per treatment group. Evaluable participants are defined as those randomized participants who receive IP and have a valid baseline and at least 1 postbaseline WAIS-IV Coding test assessment. Additional participants may be randomized if the dropout rate is higher than 20%.

Table 6 summarizes operating characteristics of this design based on 120 evaluable participants.

Repeated Analyses	Information Time	No of Participants	Boundaries for Efficacy	Boundary for Futility
Interim	0.5	60	2.796	0.4229
Final	1	120	1.977	

Table 6:	Group Sequential Design
----------	-------------------------

13.8.1.

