The primary endpoint is change from baseline to Day 84 in the WAIS-IV Coding test and this primary endpoint will be analyzed using a mixed-effects model for repeated measures (MMRM). The model will include baseline WAIS-IV Coding test score as a continuous explanatory variable, treatment, visit, and visit-by-treatment interaction as categorical explanatory variables. The Kenward-Roger correction to degrees of freedom will be applied. All explanatory variables will be treated as fixed effects in the model, and all post-baseline time points will be included in the model. An unstructured (UN) covariance matrix with the default Newton-Raphson algorithm as implemented in the SAS procedure PROC MIXED will be used to model the within-subject correlation. If this model fails to converge, the Fisher Scoring algorithm (via the SCORING option of the PROC MIXED statement), the no-diagonal factor analytic structure (via the TYPE=FA0(T) option of the REPEATED statement, where Tis the total number of time points), Toeplitz (TOEP), Autoregressive (1) [AR (1)], Compound symmetry (CS) covariance structure will be used, following this sequence until convergence is achieved. If the model still does not converge with CS structure, no results will be reported. When the covariance structure is not UN, the sandwich estimator for the variance-covariance matrix will be derived, using the EMPIRICAL option in the PROC MIXED statement in SAS. The primary comparison will be between SAGE-718 and placebo at the Day 84. The LSM and SE with 95% CI for each treatment group as well as difference in LSM and SE with 95% CI will be summarized, and the p-value from the hypothesis test of no difference between the treatment groups will be also presented.

Descriptive statistics of WAIS-IV Coding test score, percent change from baseline and change from baseline will be summarized by treatment group and by visit.

Line plots with LSM and SE bars of change from baseline in WAIS-IV Coding test score over time by treatment group will be provided.

By-participant listing of WAIS-IV Coding test score by treatment group and by visit will be produced.

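### Do the printed stopping boundaries conflict with the spending-function wording, and is the final critical value unclear if no interim is run?

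*SAP*

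**What the plan says.** SAP 5.2 plans 120 evaluable participants for 90% power to detect a difference of 2.5 points with SD 4.2, and states: "This sample size and power are based on a 2-sided t-test using an overall significance level of 0.05". One interim "may be conducted after approximately 60 participants as total have completed Day 84 (Week 12"). On the method it says that the "group sequential method by O'Brien and Fleming for the two-sided test will be used", and then: "The significance level will be based on the type I error spending function of Lan and DefsMets". Table 2 gives interim and final efficacy boundaries of 2.796 and 1.977 at information times 0.5 and 1. Protocol 13.8 (Table 6) and the synopsis print the same values, with the level "based on the type I error spending function of Lan and DeMets such that the overall significance level will be maintained at 0.05". None of the three places gives the form of the spending function.

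The Protocol Amendment 1 rationale says that an interim is not currently planned because enrolment was fast, and that the interim portion "will remain in the sample size section of the protocol and will be addressed in the SAP". It also says: "The final analysis will be performed at the 2-sided significant level of 0.05".

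SAP 8.3.3.1 asks for least squares means, 95% confidence intervals and a test, with the instruction that "the p-value from the hypothesis test of no difference between the treatment groups will be also presented". It names no critical value. SAP 8.3.3.2 records multiplicity adjustment as not applicable.

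**The concern.** There are two separate worries.

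The first is the interim. Classical O'Brien-Fleming boundaries are computed for a fixed schedule of looks. A spending function recomputes them at the information actually reached. The interim falls at about 60 participants, so the information fraction would rarely be exactly 0.5. Two statisticians reading the same paragraph could reach different stopping boundaries. At 0.5 the nominal two-sided p needed to stop would be 0.0052 on one reading and 0.0031 on the other.

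The second is the final test. If no interim is run, the amendment rationale points to 0.05 (critical value 1.960), while the only final boundary printed in the visible SAP is 1.977. A p-value between 0.048 and 0.050 would then be positive on one document and negative on the other, in a trial with a single primary endpoint.

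**Working it through.** **Inputs** (SAP 5.2, Protocol 13.8): difference 2.5; SD 4.2; 60 per arm; two-sided alpha 0.05; interim at 60 of 120 (30 per arm); boundaries 2.796 and 1.977. All results are on the normal scale.

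**1. The plan's sample size.** n per arm = 2(1.960 + 1.282)² × (4.2/2.5)² = 2 × 10.507 × 2.8224 = 59.3, rounded up to 60, so 120 in total; 120/(1 − 0.2) = 150 randomized. Both agree with the plan. The expected final Z is 2.5/(4.2 × √(2/60)) = 3.260, and single-look power is Φ(3.260 − 1.960) = 90.3%.

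**2. The printed boundaries.** Under the null, the interim and final statistics are bivariate normal with correlation √0.5 = 0.7071. Solving P(|Z1| > C√2 or |Z2| > C) = 0.05 gives C = 1.9774, and 1.9774 × 1.4142 = 2.7965. Table 2 is therefore classical two-look O'Brien-Fleming. The rounded pair 2.796/1.977 has overall alpha 0.0501 and power 90.1%.

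**3. The usual spending form.** O'Brien-Fleming-type spending with 0.025 per side spends 2 − 2Φ(2.241/√t) by information t. At t = 0.5 this is 2 − 2Φ(3.170) = 0.001525 per side, or 0.00305 two-sided. The boundaries become 2.963 and 1.969, with power 90.2%. The same function applied to the total 0.05 gives 2.772 and 1.979. Neither is the printed pair, but a function that spends 0.00517 at 0.5 would reproduce it.

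**4. The interim hurdle in points.** The standard error at 30 per arm is 4.2 × √(2/30) = 1.0844. The hurdle is 2.796 × 1.0844 = 3.03 points, against 2.963 × 1.0844 = 3.21. The chance of stopping early for efficacy under the design assumptions is 31% against 26%.

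**5. Interim away from 0.5.**

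| Interim at | Information | O'Brien-Fleming-type spending | Classical form, retimed | Alpha if 2.796/1.977 kept unchanged |
|---|---|---|---|---|
| 54 of 120 | 0.45 | 3.144 / 1.965 | 2.939 / 1.971 | 0.0504 |
| 60 of 120 | 0.50 | 2.963 / 1.969 | 2.7965 / 1.9774 | 0.0501 |
| 66 of 120 | 0.55 | 2.806 / 1.974 | 2.676 / 1.984 | 0.0497 |

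The two middle columns hold alpha at 0.05 by construction. The last column is the least careful reading, and it departs from 0.05 by at most 0.0004.

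**6. No interim.** A critical value of 1.960 gives alpha 0.050 and power 90.3%. A value of 1.977 gives alpha 0.048 and power Φ(3.260 − 1.977) = 90.0%. The probability that the final Z lies between them under the design assumptions is 0.9032 − 0.9003 = 0.003.

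**The case for a change.** The strongest case for a change is that a primary significance threshold should not be left to inference. The amendment handed the interim to the SAP, yet the visible SAP neither names the spending function nor says that Table 2 lapses without an interim. An interim difference between 3.03 and 3.21 points would stop the trial on one reading and let it continue on the other. Anyone who ran the interim at 2.796 and then tested the final analysis at 1.960, citing the amendment rationale, would have an overall alpha of 0.0520.

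Part of this stands. The function is unnamed, its boundaries cannot be recomputed from the visible text, and the no-interim level is not restated there.

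The rest is weaker. No passage fixes the printed values at other information fractions: Table 2 is presented as the operating characteristics at 0.5, and classical boundaries would themselves be retimed. The two sentences need not contradict each other, since some spending functions agree with the table, and moving to 2.963/1.969 would be a choice among options. The 0.0520 case combines an interim with a level that the amendment states for a design from which the interim has been removed. It would also breach the requirement, in both documents, that the overall level stay at 0.05.

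The apparent conflict over the final level also has a plain resolution. Table 2 describes a two-look design, so with one look an overall two-sided 0.05 is 1.960. SAP section 6.1 declares no modifications from the protocol.

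**Conclusion.** No change is needed. Every printed boundary is correct for the O'Brien-Fleming method that the plan names, and every reasonable reading leads to a sound test. Alpha lies between 0.048 and 0.0504 with no interim or with one at information 0.45 to 0.55, and power varies by 0.3 percentage points or less. What is missing is descriptive: the form of a spending function, and a restatement in the SAP of a final level that the amendment rationale already gives. A statistician running the interim would have to settle the function before looking at the data, and either choice protects the overall level.

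The interim question also looks remote. The amendment says none is currently planned, SAP section 2 describes the SAP as being for the final analysis, and SAP 8.2.1 already refers to enrolment having closed.

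This conclusion assumes the normal approximation, the plan's difference and SD, an interim (if any) close to half the information, and the amendment rationale as the governing statement for the no-interim case. It concerns the visible text only; SAP section 9 is blank in the public copy and may cover the interim.
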